**What is considered as an Unexpected Grade 4 event?**

Any grade 4 event that was not specifically listed as an expected adverse event in the protocol should be considered as unexpected. A grade 4 adverse event can be considered to be unexpected if it is an event that would not be expected based on the treatment being received or if it is unexpected based on the health of the patient. In either case, if there is any uncertainty about whether a grade 4 adverse event is expected or unexpected it should be reported to DSMC.

**DSMC notification responsibilities of the person (e.g., nurse) handling the reporting/documenting of the SAE in WISER:**

1. Make a phone call (or speak in person) to the appropriate clinical member of the DSMC according to the schedule as listed below (page if necessary).
2. Enter a new SAE into the SAE module that is located in the Subject>> CRA Console in WISER WITHIN 24 HOURS of first knowledge of the event. Information can be entered and saved, but the DSMC members will not be notified until a date is entered into the DSMC Notification Date Field. This will ensure that all persons that need to be made aware of the event (i.e., PI, study team members and DSMC members) will be notified; remember to file a copy of the confirmation.
3. Document that the appropriate person(s) on the DSMC has been contacted. Indicate the name of the DSMC clinician that was contacted and the date and time contacted in the Event Narrative field in the SAE console of the particular subject.
4. Document whether or not the protocol should be suspended based on the discussion with the DSMC clinician. This is the major function of the email notification. Enter whether the protocol should be suspended in the Event Narrative Field.
5. Follow up/update the clinical member(s) of DSMC regarding any new developments or information obtained during the course of the SAE investigation and reporting process.

**Elements needed to complete the SAE form in the Subject Console in WISER (see Screen Shot 3):**

1. Event Date
2. Reported Date
3. Reported by
4. If Grade 5, enter Death Date
5. If Grade 5, enter Death occurred: within 30 days
6. Event Narrative: Brief description (include brief clinical history relevant to this event, including therapies believed related to event). Begin narrative with the DSMC clinician who was notified and Date/Time notified. In addition, state attribution by DSMC clinician as either "Unrelated", "Unlikely", "Possibly", "Probably", or "Definitely". Always include the following here:
  - i. DSMC clinician name, date/time contacted and comments
  - ii. Date of last dose before the event

[figure not shown]
A Randomized Trial of Consolidative Immunotherapy with vs without Thoracic Radiotherapy and / or Stereotactic Body Radiation Therapy (SBRT) after First-line Systemic Therapy for Metastatic NSCLC  
Wake Forest Baptist Comprehensive Cancer Center  
WFBCCC # 62718

iii. Is suspension of the protocol needed? Y/N

7. Treating Physician comments
8. PI comments, if available
9. Protocol Attribution after discussion with DSMC clinician
10. Outcome (Fatal/Died, Intervention for AE Continues, Migrated AE, Not Recovered/Not Resolved, Recovered/Resolved with Sequelae, Recovered/Resolved without Sequelae, Recovering and Resolving)
11. Consent form Change Required? Y/N
12. SAE Classification **\*This is required in order for the email notification to be sent\***
13. Adverse Event Details – Enter all details for each AE associated with the SAE.
  - a. Course start date
  - b. Category
  - c. AE Detail
  - d. Comments
  - e. Grade/Severity
  - f. Unexpected Y/N
  - g. DLT Y/N
  - h. Attributions
  - i. Action
  - j. Therapy
  - k. Click ADD to attach the AE Detail to the SAE.
14. Enter Date Notified DSMC -- **\*This is required for the email notification to be sent\***
15. Click Submit. The auto-generated notification email will disseminate within 5 minutes. If you do not receive an email within 5 minutes, check that you have entered the “Date Notified DSMC” and the “SAE Classification”. If these have been entered and the email still has not been received, take a screen shot of the SAE in WISER and immediately email it out to all of the STRC members listed in this SOP. In the subject line, indicate that this is a manual transmission of the SAE in lieu of the auto-generated email. It is required that a notification goes to the DSMC members immediately so that their assessment can be obtained within the 24 hour period requirement. Contact the Cancer Center Programmer/Analyst to alert that there is an issue with the auto-generated email.

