**9.0 Adverse Events List and Reporting Requirements**

**9.1 Adverse Event List for Radiotherapy**

Risks and side effects related to the SBRT	
More common (>10% of patients): 
 
Damage to surrounding normal lung and/or collapse of a portion of treated lung
 
Cough
 
Increased phlegm production
 
Changes in the lungs as the tumor shrinks; these changes will be recognized by your radiation doctor on your x-rays or scans as expected "scarring" that is developing. In most patients, no noticeable symptoms will result from this lung damage.
 
Fatigue
 
Redness of irritation of the skin in the treatment area
 
Hair loss in the treatment area
 
Some soreness of the ribs with an increased risk of rib fracture.
 
	Less common (<10% of patients): 
 
Difficulty breathing, increased shortness of breath
 
Fever
 
Fracture or compression of the treated bones of the spine, which can result in pain and may need surgical treatment
 

Rare (<1% of patients)	

Some patients can have the following symptoms associated with lung scarring:
 
 
Shortness of breath, cough, fever, and/or pain in the chest wall.
 
These patients may require oxygen for a short time or permanently.
 
Lung damage can be life threatening.
 
Pericarditis
 
Damage to the heart muscle, which can cause heart attack, heart failure, or death
 
Damage to the spinal cord, which can cause numbness, weakness, tingling, and/or inability to use the arms and/or legs
 
Damage to the esophagus, which can cause problems with swallowing
 
Damage to the stomach or bowel which can lead to ulceration or perforation with a risk of infection and death.
 
Damage to the large blood vessels surrounding the heart, which could cause coughing up of blood and possibly death
 
Severe pain or skin damage leading to an open wound.
 
The following are likely with SBRT to the bones of the spine in the neck:
 
Inflammation of the lining of the mouth and esophagus
 
Inflammation of the vocal cords, leading to hoarseness or loss of voice
 
	
Risks and side effects related to non-SBRT or more "fractionated" radiation to the chest:	

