**14.2 Analysis of Secondary Objective**

The proportions with local control (LC) of SBRT-treated lesions, and overall survival (OS) parameter estimates, both secondary outcomes, will be first examined in simple univariate and bivariate analyses (e.g., means, medians, 85% confidence intervals around key parameter estimates.). LC will be assessed only in patients with at least 4-months of radiographic follow -up. The reason for specifying a minimum of 4 months follow-up to score LC was to avoid uncertainty associated with early transient radiographic changes within the high dose region; patients who died without a minimum of 4 months post-SBRT imaging study follow-up are not considered evaluable for LC but are evaluable for PFS and OS.

Data will be collected for planned subset analysis of in-field local control of irradiated sites, progression-free and overall survival according to (1) tumor histology (adenocarcinoma vs other histology) and (2) response to initial chemotherapy (response vs stable disease).

In all randomized patients, time to progression at known sites of disease, as well as time to development of new disease sites, and number of new disease sites will be collected.

Overall survival comparison between the two randomized groups will be assessed with methods analogous to PFS described above in 13.1. Additionally, we will also examine OS in the group of patients who were enrolled but not randomized; however, we will not conduct statistical comparisons of this group with either randomized group.

All safety measures, including acute and late toxicity, will be reported using descriptive statistics (mean, median, SD, proportions, and 95% confidence intervals). This will include calculating frequency/risk of adverse events by treatment site. Potential toxicities reported would include pneumonitis, esophagitis, chest wall pain, dermatologic toxicity, renal dysfunction, gastrointestinal toxicity including nausea, vomiting, and diarrhea, hepatotoxicity, and abdominal pain. These toxicities would be assessed according to site of irradiation by the treating physician and graded as per CTCAE 5.

A Randomized Trial of Consolidative Immunotherapy with vs without Thoracic Radiotherapy and / or Stereotactic Body Radiation Therapy (SBRT) after First-line Systemic Therapy for Metastatic NSCLC  
Wake Forest Baptist Comprehensive Cancer Center  
WFBCCC # 62718

Reference List

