**Appendix L: Survival Form**

**Instructions:** Fill this form out at protocol indicated survival assessments

1. Last known Survival Status:  
 Alive  
 Dead  
 Lost to Follow-up: Date of last contact \_\_\_\_/\_\_\_\_/\_\_\_\_ (MM/DD/YYYY)
2. Expired Date \_\_\_\_/\_\_\_\_/\_\_\_\_ (MM/DD/YYYY)  
Is this an approximate date?  Yes  No
3. Last known Alive Date \_\_\_\_/\_\_\_\_/\_\_\_\_ (MM/DD/YYYY)
4. Survival Status source: \_\_\_\_\_  
*Instructions: Source can be EMR, obituary, family member etc. Phone call with patient  
Add to comments in WISER follow-up section*
5. Comment: \_\_\_\_\_

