**Appendix M: Study Withdrawal**

PID Number _____	DOB _____
1. Date Study Treatment Stopped or Withdrawal _____/____/____ (MM/DD/YYYY)	
2. Please check ONE of the following:  Patient did not complete radiation therapy  Patient withdrew or discontinued early	
3. If withdrawn or discontinued early, indicate ONE primary below:  Patient registered but not treated: Specify reason: _____  Radiotherapy attempted, but not completed  Progression during treatment  Unanticipated Adverse Event/Serious Adverse Event  Patient Died: Date of Death ____/____/____ (MM/DD/YYYY)  Unknown date Specify Cause of Death: _____  Unknown cause  Lost to follow-up: Date of Last Contact ____/____/____ (MM/DD/YYYY)  Unknown : Date Last Known to be Alive ____/____/____ (MM/DD/YYYY)  Patient no longer willing to participate in study	

A Randomized Trial of Consolidative Immunotherapy with vs without Thoracic Radiotherapy and / or Stereotactic Body Radiation Therapy (SBRT) after First-line Systemic Therapy for Metastatic NSCLC  
Wake Forest Baptist Comprehensive Cancer Center  
WFBCCC # 62718

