**Appendix O: Off-Study Form**

Study Number: \_\_\_\_\_ PID: \_\_\_\_\_

Investigator: [name] M.D. Date \_\_\_\_/\_\_\_\_/\_\_\_\_ (MM/DD/YYYY)

**Instructions:** Complete this form if the patient has completed or is removed from the study.

Name of Person Completing form \_\_\_\_\_

Off study date \_\_\_\_/\_\_\_\_/\_\_\_\_ (MM/DD/YYYY)

Reason:

Adverse Event/Side Effects/Complications;

Death; (if death fill out Survival Form)

Enrolling Physician Decision;

Other;

Patient lost to follow-up; Date of last contact \_\_\_\_/\_\_\_\_/\_\_\_\_ (MM/DD/YYYY)

Patient refused follow-up;

Protocol-defined follow-up completed

Explain \_\_\_\_\_

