All Adverse Events (AEs) and Serious Adverse Events (SAEs) that occur on any patients enrolled on WFBCCC Investigator Initiated Interventional trials must be entered into the WISER system. The only exception to this requirement is for patients enrolled on NCORP trials at non- WFBCCC sites. AEs and SAEs for NCORP patients enrolled at WFBCCC sites must be entered into the WISER system. Once these AEs and SAEs are entered in WISER, certain actions must be taken regarding the reporting of specific Adverse Events to the DSMC.

All Adverse Events that occur during protocol intervention (defined below) and are coded as either 1) **unexpected grade 4, 2) unplanned inpatient hospitalization > 24 hours (regardless of grade)**, or **grade 5 (death)** must be reported to the DSMC using the SAE console in WISER.

A research nurse or clinical research coordinator when made aware that an adverse event meets one of the above criteria has occurred on a WFBCCC Investigator Initiated interventional trial, is responsible for informing a clinical member of the DSMC by phone (or in-person) about the adverse event. The nurse/coordinator should contact the treating physician prior to calling the DSMC clinical member to obtain all details of the SAE, as well as all associated

A Randomized Trial of Consolidative Immunotherapy with vs without Thoracic Radiotherapy and / or Stereotactic Body Radiation Therapy (SBRT) after First-line Systemic Therapy for Metastatic NSCLC  
Wake Forest Baptist Comprehensive Cancer Center  
WFBCCC # 62718

toxicities to be recorded along with the SAE. In addition, this nurse or coordinator is responsible for entering the adverse event information into the SAE console in WISER. Once the adverse event has been entered into the SAE console an email informing the entire DSMC will be generated.

**THESE REPORTING REQUIREMENTS APPLY TO any staff member on the study team for a WFBCCC Institutional Interventional trial. Ultimately, the protocol PI has the primary responsibility for AE identification, documentation, grading and assignment of attribution to the investigational agent/intervention. However, when an AE event as described above is observed, it is the responsibility of the person who observed the event to be sure that it is reported to the DSMC.**

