**What is considered during protocol intervention?**

During protocol intervention is considered to be the time period while a patient is on study treatment or during the time period within 30 days of last study treatment (even if patient begins a new (non-study) treatment during the 30 days). This window of 30 days should be the standard window to be used in all protocols unless a specific scientific rationale is presented to suggest that a shorter window can be used to identify events. If it is a trial sponsored by Industry and the sponsor requires a longer window for monitoring of SAEs, then the longer window of time specified by the sponsor should be followed.

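### Deaths after progression and more than 30 days after the last study treatment are followed only on a Survival Form with no cause or attribution item, so fatal late toxicity there is not systematically collected

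*Combined protocol and SAP*

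**What the plan says.** **Reporting commitment.** Section 14.2 states: "All safety measures, including acute and late toxicity, will be reported using descriptive statistics". The statistics it names include proportions and 95% confidence intervals. Section 9.1 lists radiation harms that can kill, for example "Damage to the large blood vessels surrounding the heart, which could cause coughing up of blood and possibly death", under the heading for rare events (<1% of patients).

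**SAE route.** Appendix R sets the trigger for reporting to the DSMC: "All Adverse Events that occur during protocol intervention (defined below) and are coded as either 1", followed by the qualifying categories, of which death is one. It defines that period as time on study treatment or "during the time period within 30 days of last study treatment". The SAE form collects a narrative, physician comments and attribution. It also has the item "If Grade 5, enter Death occurred: within 30 days".

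**After progression.** Section 8.4.2 and Study Calendar footnote 9 say that patients who progress are followed for survival only, on Appendix L. That form carries the instruction "Fill this form out at protocol indicated survival assessments". It records status, dates, the source of the information and a comment.

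**Other forms.** The Off-Study Form (Appendix O) sends deaths on: "Death; (if death fill out Survival Form". The Off Treatment form (Appendix Q) does the same. The item "Specify Cause of Death" is on Appendix M, the Study Withdrawal form, which covers incomplete radiation, withdrawal and early discontinuation.

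**The concern.** The trial adds radiation to maintenance immunotherapy, and objective 2.2.3 is to evaluate the toxicity of that addition. Some radiation harms appear late, and the most serious of them is death. If a patient progresses, leaves study treatment and later dies of such a harm, the plan schedules nobody to ask why. The patient stays in the denominator of any toxicity rate, but the event may never reach the numerator. The reported rate of fatal late toxicity can then be too low for a reason built into the forms.

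What is at stake is the completeness of a descriptive safety result, not the primary comparison.

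**Working it through.** No formula applies to the main point. The check is to follow each route by which a death can be recorded and ask whether cause or attribution is prompted.

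| Situation of the death | What the plan schedules | Cause or attribution? |
|---|---|---|
| On study treatment, or up to 30 days after it ends | SAE form (Appendix R) | Yes: narrative and attribution |
| Recorded as a study withdrawal | Appendix M | Yes: explicit cause item |
| Later, without progression | Toxicity grading at visits; Appendix J asks about late radiotherapy complications and sends a yes to the AE form; the AE log (Appendix S) holds grade 5, attribution and a died outcome | Yes, if linked to an adverse event |
| After progression and more than 30 days after the last study treatment | Appendix L only | No: an optional comment |

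The gap is the last row. Three further points bear on it.

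1. **When the window closes.** It runs from the last study treatment, not from radiation. Section 8.5 refers to a total of 2 years of maintenance immunotherapy, so the window can extend well beyond radiation. The same section lists progression among the reasons treatment ends, so for many patients the window closes soon after progression. That is also when Appendix J stops.

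2. **Section 9.4 against Appendix R.** Section 9.4 says that every grade 5 SAE goes to the DSMC and states no time limit. Appendix R applies the 30-day limit. A site could read a late fatal event as reportable under one and not under the other.

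3. **Scale.** The plan randomizes 112 patients 2:1, so the radiation arm has 112 × 2/3 = 74.7, about 75. One unrecorded death would lower the observed rate in that arm by 1/75 = 1.3 percentage points. Section 9.1 puts the relevant harms below 1%, which is fewer than 0.01 × 75 = 0.75 expected patients per listed harm, fatal or not. The documents give neither the fatal fraction nor the share occurring after progression, so the number of missed deaths cannot be derived.

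**The case against.** The strongest reply is that the plan has more routes than Appendix L. Appendix R requires all AEs and SAEs to be entered in WISER, and that sentence has no time limit. Section 9.4 has none either. The AE log can store a grade 5 event with attribution at any time. Appendices L, O and Q have free-text lines, and Section 9.6.5 requires study documentation, including source documents, to be kept for six years after completion and the final report.

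Much of this stands, and it rules out several stronger readings:

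- A reader might infer that cause is requested only inside the SAE window or on the withdrawal form, and that every other death goes unexplained. The documents do not support this. Before progression, Appendix J, the AE log and the general entry rule give a late fatal event a route with attribution.
- A reader might take the SAE form's 30-day item as the rule that bars later deaths. It is a field on the form; the rule is the definition of protocol intervention.
- A reader might conclude that these deaths can never be counted. Some could be recovered from comments or records. The supportable statement is that collection is neither structured nor systematic.
- A reader might infer that survival results are compromised. OS counts death from any cause and PFS counts progression or death, so neither needs a cause. No cause-specific survival analysis is planned.

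The reply does not close the gap itself. A log that can hold an event is not a schedule for finding it, and after progression no scheduled form prompts for cause. An optional comment is a weak basis for a proportion with a confidence interval. Appendix M could in principle be completed for a later death, but footnote 9 restricts follow-up after progression to Appendix L.

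**Conclusion.** The point holds for deaths after progression and more than 30 days after the last study treatment. Fatal late toxicity in that period is not systematically ascertained, although 14.2 undertakes to report late toxicity, so its rate may be biased downward. The effect is confined to the toxicity objective.

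The size of the bias cannot be estimated from the documents. A reader might infer a large one because many deaths in metastatic NSCLC follow progression. That share would need assumed inputs, and it would describe all deaths, most of them presumably from cancer, not the toxic deaths missed. Section 9.1's rare category points to small absolute numbers.

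One limit remains: a few pages, including Section 8.3 and Appendix N, were not in the text available for this check. The list of forms in Section 10.0 names no separate cause-of-death form, which supports the conclusion but does not prove it. This is a worthwhile, inexpensive improvement and not a flaw in the primary analysis.

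**What to change.** 1. **Appendix L:** add the cause-of-death item already on Appendix M, with coded answers: NSCLC; protocol treatment (radiation / immunotherapy / cannot separate); other; unknown.
2. **Section 14.2:** report treatment-related deaths at any time by arm as number, percentage and 95% CI, with the number of deaths of unknown cause beside them.
3. **Section 9.4 and Appendix R:** reconcile the two, so that sites know whether a grade 5 event beyond the 30-day window is reportable to the DSMC.

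The cost is one form item, one table and one clarifying sentence. Treatment, eligibility, sample size and the primary analysis do not change. The downside is imperfect attribution: some causes will be unknown or uncertain, especially after later therapies or when the source is an obituary or a family member. Showing the unknowns in the table keeps that visible.

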**Definition of Unavailable:**

As a general guideline if the first clinician that is contacted does not respond to the phone call or page within 30 minutes, then initiate contact with the next DSMC clinician listed in the table above on the particular day the SAE is being reported. Allow up to 30 minutes for the new DSMC clinician to respond to a phone call or page before contacting the next member in

A Randomized Trial of Consolidative Immunotherapy with vs without Thoracic Radiotherapy and / or Stereotactic Body Radiation Therapy (SBRT) after First-line Systemic Therapy for Metastatic NSCLC  
Wake Forest Baptist Comprehensive Cancer Center  
WFBCCC # 62718

the table. These times (30 minutes) are a general guideline. Best judgment as a clinical research professional should be used giving considerations of the time of day, severity of the SAE, and other circumstances as to when it is appropriate to contact backup clinicians. If the event occurs near the end of day, then leave messages (voice or email) as appropriate and proceed with submitting the DSMC notification form. It is important to take reasonable steps and to document that some type of contact has been initiated to one or more of the clinical members of DSMC.

